6.5. Baseline definition

For all parameters, baseline will be defined as the last available measurement prior to the IMP administration.

6.6. Duration

Duration (in days, hh:mm) will be calculated by the difference between the start and stop date and time (e.g. duration of AE [days, hh:mm] = end of AE date and time – AE onset date and time).

Duration (in days) will be calculated by the difference between the start and stop date + 1 (e.g. duration of a medication [days] = end of medication date – onset of medication date + 1).

6.7. Type I error rate

Unless stated otherwise, statistical tests will be two-sided and will be carried out at the 5 % level of significance.

7. Description of study subjects

7.1. Definition of analysis sets

The following analysis sets will be defined:

- Screened set: all of the subjects having signed an informed consent form (ICF).
- Included set (IS): all the included participants who have signed an ICF.
- Randomised set (RS): all the randomised participants.
- Safety set (SS): all the included participants who have received at least a partial dose of IMP (Ir-CPI or placebo).
- Pharmacodynamic set (PDS): all the included participants who have completed the study without any protocol deviation affecting PD evaluation and with at least one available post-baseline PD data.
- Pharmacokinetic set (PKS): all of the included participants who have been administered a complete infusion of IMP without major protocol deviation affecting PK evaluation. The inclusion of the subjects with incomplete PK profile(s) or incomplete infusion will be discussed before the PK concentration dataset is locked.

The analysis sets will be precisely defined and validated during the blind review meeting.

The safety and pharmacokinetic sets will be analysed using subjects as treated. The randomised and pharmacodynamic sets will be analysed using subjects as randomised.

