5.2. Number of Participants

In any part of this trial, if it is decided that additional data are needed to better define the safety and tolerability or PK/PD of Ir-CPI, additional panels of healthy male participants may be enrolled per amendment. For example, a given dose level may be repeated in newly enrolled participants, or a lower or intermediate dose may be administered based on emerging data.

Participants who drop out for safety and tolerability reasons will not be replaced; participants withdrawing for other reasons might be replaced. Replacement participants will be assigned to the same treatment group as the participants they are replacing (as shown in Table 4).

Randomised participants who discontinue after having been exposed to the study drug may be replaced, if this discontinuation is not related to safety issues. The decision to replace participants will be made on a case-by-case basis.

The data collected on the withdrawn participant prior to withdrawal will be included in the statistical analyses.

5.2.1. Part 1

Approximately forty (40) healthy male participants will be enrolled in five (5) sequential panels (A-E). Each panel will have eight (8) participants (6 active: 2 placebo). The fifth group will be optional depending on the PK and PD data obtained in the previous groups. In the end, this group was not performed.

5.2.2. Part 2

Approximately twenty-four (24) healthy male participants will be enrolled in three (3) sequential panels (F-H). Each panel will have eight (8) participants (6 active: 2 placebo). In the end, this part was not performed.

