8. DISCONTINUATION CRITERIA AND RELATED PROCEDURES

8.1. Withdrawal criteria

Any participant may be withdrawn from the study at the discretion of the Investigator. The participant is also free to terminate his participation at any time. However, if the participant has been dosed with study medication, it is recommended to ask the participant to remain in contact with the centre, and the investigational site should make every effort to convince the participant to return for a safety visit (corresponding to the discharge visit) and a laboratory sample taken to look for immunogenicity (presence of anti-drug antibodies and neutralizing antibodies if applicable).

The Investigator will also undertake to obtain more detailed information about any participant who is lost to follow-up.

Participants who are withdrawn from the study must not be re-included.

The eCRF must document the primary reason for withdrawal.

Investigators should contact the Medical Monitor, whenever possible, to discuss the withdrawal of a participant in advance.

Supplemental ADA samplings (“long-term follow-up of ADAs”):

These procedures do not apply for the additional samplings performed after D180.

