10.2.9.2. Statistical methodology

Analysis of exploratory parameters will be performed on the Pharmacodynamic set.

For each parameter, descriptive statistics will be provided by treatment group on values and changes from baseline for each timepoint. Graphs over time by treatment group will be also produced.

Presence of ADAs will be described by treatment group and timepoint until D180.

All exploratory parameters will be listed.

Supplemental ADA samplings ("long-term follow-up of ADAs"):

Results after D180 will be listed when applicable and the listing will be appended to the final CSR.

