Linear dose-proportionality will be concluded if the two-sided 90 % confidence interval (CI) for the slope value of the log-transformed dose is within the critical $[(1+\ln(LL)/\ln(r)) ; (1+\ln(UL)/\ln(r))]$ region, where $r = \text{Dose Maximum/Dose Minimum}$, $LL = 0.8$ and $UL = 1.25$ [2].

The following SAS® code will be used:

```
proc mixed data=ADPP method=REML;
  by PARAMCD;
  class USUBJID;
  model ln(AVAL) = ln(dose) / solution cl alpha=0.10 ddfm=kr;
  random USUBJID;
run;
```

10. Pharmacodynamics data

The pharmacodynamic analysis will be performed on the PDS set.

PD aPTT, Factor XI and Factor XII inhibition will be measured by the change from baseline (central lab). PD aPTT and FXI/FXII parameters will be measured (see section 16.1):

- For cohorts A, B and C:
 - on D1, pre-dose then at 30min, 60min, 90min, 2h, 4h, 6h, 6h30, 7h, 7h30, 8h, 10h, 12h, 16h post-dose, then on D2 (24h), D3 (48h), D4 (72h), D5 (96h) and discharge visit (D10 ± 2 days) (see section 16.1).
In case of infusion less than 6 hours and besides assessment at pre-dose, 30 min, 60 min, 90 min, 2h and 4h after start of infusion, parameters should be measured at the end of infusion, then 30min, 60 min, 90min, 2h, 4h, 6h, 10h, then 18h, 42h, 66h and 90h after the end of infusion and then at the discharge visit.
- For cohort D:
 - on D1, pre-dose then at 30min, 60min, 90min, 2h, 4h, 6h, 6h30, 7h, 7h30, 8h, 10h, 12h, 16h post-dose, then on D2 (24h), D3 (48h), D4 (72h), D5 (96h), D7 (144h) and discharge visit (D10 ± 2 days) (see section 16.1).
In case of infusion less than 6 hours and besides assessment at pre-dose, 30 min, 60 min, 90 min, 2h and 4h after start of infusion, parameters should be measured at the end of infusion, then 30min, 60min, 90min, 2h, 4h, 6h, 10h, then 18h, 42h, 66h, 90h and 138h after the end of infusion and then at the discharge visit.

For each time point, including the baseline time point, an aPTT ratio will be calculated by dividing the aPTT value (in sec) of the specific time point (aPTT*) by the baseline aPTT value (in sec) (aPTT°) of the same volunteer (aPTT ratio = aPTT*/aPTT°). The baseline time-point is considered as having an aPTT ratio of 1. A graphical representation of aPTT ratio in function of the time will be done per volunteer. The mean ± SEM, min and max curves will be also represented for each cohort on separate graphs. The mean ± SEM curves of all cohorts (A, B, C, D) will be also represented on one graph.

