Concerning FXI and FXII PD parameters, a graphical representation of individual data of FXI activity in each cohort, in function of the time, will be done. Another graphical representation of FXII activity in each cohort, in function of the time, will be done. In these graphs, the normal lower ranges of FXI and FXII activities will be indicated as horizontal lines.

Moreover, FXI or FXII inhibition, expressed in percentages, for each time point (including the baseline time point), has to be calculated for each volunteer. To do so, the calculation is the following:

- Percentage of FXI inhibition= $(100 - ((FXI^*/FXI^\circ) * 100))$
- Percentage of FXII inhibition= $(100 - ((FXII^*/FXII^\circ) * 100))$

FXI* or FXII*: FXI or FXII percentage of inhibition of a specific time point

FXI° or FXII°: FXI or FXII percentage of inhibition of the baseline time point

The baseline time point is considered as 0 % of FXI or FXII inhibition. A graphical representation of FXI or FXII inhibition, expressed as percentages, in function of the time will be done per volunteer. The mean \pm SEM, min and max curves will be also represented for each cohort on separate graphs. The mean \pm SEM curves of all cohorts (A, B, C, D) will be also represented on a same graph.

Descriptive statistics of changes from baseline will be provided by treatment group and each measurement time for changes from baseline of aPTT ratio and absolute values.

Descriptive statistics will be provided by treatment group on each measurement time for aPTT values (absolute values and changes from baseline), aPTT ratio (ratio values and changes from baseline of ratios) and percentage of FXI or FXII inhibition (calculated percentages and changes from baseline of percentages).

All pharmacodynamics parameters will be listed.

11. Exploratory Pharmacokinetic / Pharmacodynamic analysis

Evaluation of the relationship between concentrations of Ir-CPI and the PD parameters: the change from baseline in coagulation parameters (i.e. aPTT ratio) defined above, FXI and FXII inhibition will be graphically investigated and displayed. The analysis will be performed on the PDS.

12. Exploratory Biomarkers Evaluation

The exploratory biomarkers evaluation will be performed on the PDS.

The following exploratory outcome measurements are defined:

- In blood: D-dimers, fibrinogen, prothrombin time PT (expressed in seconds and as INR), TNF α , hsCRP, cystatin C (CysC), ADA.

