14.2.2	Pharmacodynamics data

[figure not shown]
NUMBER	TITLE
14.2.2.1	Pharmacodynamic parameters for Ir-CPI – Pharmacodynamic set
14.2.2.2	Graphs of aPTT ratio means (\pm SEM), min and max curves over time by treatment groups – Pharmacodynamic set
14.2.2.3	Graphs of aPTT ratio means (\pm SEM) over time – Pharmacodynamic set
14.2.2.4	Graph of FXI and FXII inhibition means (\pm SEM), min and max values over time by treatment groups – Pharmacodynamic set
14.2.2.5	Graph FXI and FXII inhibition means (\pm SEM) values over time – Pharmacodynamic set
14.2.2.6	Individual aPTT ratio, FXI and FXII activities, FXI and FXII inhibition profiles (spaghetti plots) over time by treatment groups – Pharmacodynamic set
14.2.3	Exploratory analysis
14.2.3.1	Exploratory analysis Pharmacokinetic / Pharmacodynamic analysis
14.2.3.1.1	Graph of the relationship between treatment groups and concentrations of Ir-CPI and the change from baseline in coagulation parameters – Pharmacodynamic set
14.2.3.2	Exploratory Biomarker's Evaluation
14.2.3.2.1	Biomarker parameters for Ir-CPI – Pharmacodynamic set
14.2.3.2.2	Graphs of biomarker means (\pm SEM) over time for Ir-CPI by treatment group – Pharmacodynamic set
14.2.3.2.3	Presence of ADA and their titration for ADA+ samples – Pharmacodynamic set
14.2.3.2.4	Sub-classes determination – Pharmacodynamic set
14.3	Safety data
14.3.1	Adverse events
14.3.1.1	Adverse events – Safety set
14.3.1.2	Treatment-emergent adverse events
14.3.1.2.1	Treatment-emergent adverse events – Safety set
14.3.1.2.2	Treatment-emergent adverse events by intensity – Safety set
14.3.1.2.3	Treatment-emergent adverse events by causality – Safety set
14.3.1.3	Adverse events of special interest – Safety set
14.3.2	Listing of deaths, other serious and significant adverse events – Safety set
14.3.3	Clinical laboratory data
14.3.3.1	Haematology
14.3.3.1.1	Summary statistics – Safety set
14.3.3.1.2	Listing of subjects presenting abnormal values – Safety set
14.3.3.1.3	Number and percentage of subjects with PCSA values – Safety set
14.3.3.1.4	Shift tables (PCSA values) – Safety set

NUMBER	TITLE
14.3.3.1.5	Listing of subjects presenting PCSA values – Safety set
14.3.3.2	Blood chemistry
14.3.3.2.1	Summary statistics – Safety set
14.3.3.2.2	Listing of subjects presenting abnormal values – Safety set
14.3.3.2.3	Number and percentage of subjects with PCSA values – Safety set
14.3.3.2.4	Shift tables (PCSA values) – Safety set

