3.2. PK-PD analysis

The pharmacokinetic-pharmacodynamic analysis will be performed on the Pharmacodynamic set (PDS) defined in the final SAP as all the included participants who have completed the study without any protocol deviation affecting PD evaluation and with at least one available post-baseline data.

Subjects receiving placebo will be included in the summary and analysis of PK-PD relationship.

The rationale for PK/PD analysis is to link pharmacokinetics and pharmacodynamics in order to establish and evaluate dose-concentration-response relationships and subsequently describe and predict the effect-time courses resulting from a drug dose. PK-PD relationship will be investigated mainly to assess potential correlation between Ir-CPI exposure and the aPTT ratio.

The pharmacokinetic-pharmacodynamic analysis dedicated to FXI and FXII responses will be investigated (or not if considered not appropriate) based on exploratory analysis of the main SAP.

The preliminary graphical exploration will be performed in order to assess the effect of Ir-CPI on aPTT ratio with the dose, the pattern of the relationship for the previous PD model, the linearity assumption and the potential hysteresis between concentrations and response.

The model development will be based on the evaluation of the relation between effect and concentration using non-linear regression from model of the Phoenix WinNonlin library. A direct effect relationship was assumed for aPTT according to the safety aPTT data from interim analysis.

To compare structural models, the evaluation of the goodness of fit and the estimated parameters will be based, but not only, on the Akaike information criterion, the coefficient of variability (CV) of the parameter estimates, the random distribution of residuals between measured and predicted concentrations with respect to time, correlation between independent model parameters (<0.95) will be checked.

Plots of concentration-effect relationship between concentrations versus the corresponding aPTT ratio after Ir-CPI administration will be presented graphically with the PK-PD model selected to best fits the observed data (observed and fitted data).

Relevant PK-PD parameters estimated from the selected model will be described.

4. ADA analysis

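### The Pharmacodynamic set requires study completion, so unless blind review changes it, dosed participants who leave early drop out of PD, PK/PD, biomarker and main-SAP ADA summaries despite valid samples

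*SAP*

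**What the plan says.** SAP 7.1 defines the PDS as "all the included participants who have completed the study without any protocol deviation affecting PD evaluation", who also have at least one available post-baseline PD value. Protocol 10.2.3.1 has the same definition. Neither names a visit.

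The set is used widely:

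- PD (aPTT, FXI, FXII), SAP section 10: "The pharmacodynamic analysis will be performed on the PDS set".
- PK/PD, SAP section 11, and section 3.2 of the SAP appendix dated 13 August 2020: "The pharmacokinetic-pharmacodynamic analysis will be performed on the Pharmacodynamic set (PDS) defined in the final SAP".
- Exploratory coagulation, inflammatory and renal biomarkers and ADA. SAP section 12 says "The exploratory biomarkers evaluation will be performed on the PDS", following Protocol 10.2.9.2: "Analysis of exploratory parameters will be performed on the Pharmacodynamic set".
- The main SAP's ADA outputs, 14.2.3.2.3 ("Presence of ADA and their titration for ADA+ samples – Pharmacodynamic set") and 14.2.3.2.4.
- The individual listings of PD values (16.2.6.1) and biomarker values (16.2.6.2).

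On leavers, Protocol 5.2 states: "The data collected on the withdrawn participant prior to withdrawal will be included in the statistical analyses". Protocol 8.1 wants dosed participants who withdraw to "return for a safety visit (corresponding to the discharge visit) and a laboratory sample taken to look for immunogenicity".

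SAP 7.1 leaves the precise definition and validation of all sets to the blind review meeting. It adds a clause for incomplete cases to the Pharmacokinetic set (PKS), but not to the PDS.

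**The concern.** The other two conditions, a post-baseline PD value and no deviation affecting PD evaluation, already decide whether a participant's PD data are usable. The completion condition only removes people who left, whatever the quality of their samples.

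Leaving is a post-dose event, so the exclusion can be related to what the drug did. An adverse event is a listed reason for withdrawal (Protocol 8.6), and SAP 13.1 plans a listing of events that led to it. Participants who withdraw for a moderate or severe event are not replaced (Protocol 8.7), whereas others may be (Protocol 5.2).

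The outputs concerned include serum cystatin C, KIM-1 and NGAL, in a programme whose animal studies found kidney toxicity (Protocol 3.2). They also include ADA, for which Protocol 8.1 makes a point of asking leavers back. A sample obtained that way would not be counted in the main SAP's ADA tables.

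**Working it through.** The plan gives no power, precision or dropout figure for this point, so there is nothing of its own to reproduce. The check is a reading of the set definitions, followed by simple counts.

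**1. The three sets side by side (SAP 7.1)**

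| Set | Dosing condition | Study completion required? | Clause for incomplete cases? |
|---|---|---|---|
| Safety | at least a partial dose | no | not needed |
| PKS | complete infusion | no | yes, discussed before the concentration data are locked |
| PDS | none stated | yes | no |

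A participant who receives the full infusion and then leaves stays in the safety summaries and, absent a major deviation affecting PK, in the PK summaries. The PDS alone drops him.

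**2. What completion could mean.** Completers are counted in the disposition table (Protocol 10.2.3.2, SAP 7.2), but no visit is attached to the term. Protocol 5.4 ends the study at D90, or D180 if ADAs are detected. It puts total participation at about 18 weeks (up to 31 with D180) and treats screening to discharge as only the main part. That leans towards D90 or D180, but nothing links it to PDS membership.

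**3. Gap between the last PD sample and D90.** The last scheduled PD sample is at discharge, D10 ± 2 days, so D8 to D12. The D90 visit has a ±7 day window, so D83 to D97.

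- Shortest gap: 83 − 12 = 71 days.
- Longest gap: 97 − 8 = 89 days.

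On this reading a participant with every PD sample can be excluded for missing a visit at which no PD sample is due.

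**4. How little need be missing on any reading.** Central-laboratory PD samples (SAP section 10):

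- Cohorts A to C: 14 on D1 (predose to 16 h) + 4 (D2 to D5) + 1 (discharge) = 19.
- Cohort D: D7 is added, giving 20.

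A participant in cohorts A to C who leaves after D5 and does not attend discharge has 18/19 = 94.7% of the samples. One in cohort D who leaves after D7 has 19/20 = 95.0%. Both also have all 4 urine collections (predose, 0–6, 6–12 and 12–24 h). Neither is a completer, whether completion means discharge, D90 or D180.

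**5. Size of one exclusion.** Each panel has 6 active and 2 placebo participants, and four panels were run.

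- Active dose group: 1/6 = 16.7%.
- Pooled placebo: 4 × 2 = 8, so 1/8 = 12.5%.
- SEM at equal SD, 5 instead of 6: √(6/5) = 1.095, about 10% wider.

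These are net losses only if the leaver is not replaced.

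**6. Visibility.** Listing 16.2.3 shows who was excluded and why, but not the values. Listings 16.2.6.1 and 16.2.6.2 are on the PDS, while plasma concentrations, adverse events and safety laboratory data are listed on the Randomised set. An excluded participant's PD and biomarker values would therefore appear in neither the summary tables nor these listings.

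**The case against.** The strongest reply is that SAP 7.1 defers the exact sets to a blind review before lock, so the exclusion is not settled. That stands as a limit on certainty: a reader might infer that leavers will be omitted, and the documents do not establish that. It does not remove the problem, because the criterion given to the meeting itself excludes leavers and only the PKS has a rule for incomplete cases.

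A reader might also infer that the SAP departs from the protocol. It does not: SAP 7.1 reproduces Protocol 10.2.3.1. The tension lies inside the protocol, between the general sentence in 5.2 and the specific set definition in 10.2.3.1. The Safety set honours 5.2 for safety data, and the PKS largely does so for PK. Nor do the PDS-based listings contradict the plan, since sections 10 and 12 are PDS analyses throughout.

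The route to an informative exclusion is narrow. Stopping the infusion is not withdrawal and PK/PD sampling is meant to continue (Protocol 8.2). The PDS does not require a complete infusion, and treatment required for an adverse event is allowed (Protocol 7.11). Moreover, the near-complete profiles in the working need not belong to participants who left for an adverse event; nothing shows that a missed late visit relates to PD response. All of this stands and limits the weight of the point.

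For ADA, section 4 of the August 2020 appendix says all data will be listed, and appendix n°2 of November 2020 groups participants by any positive result. Neither names an analysis set. The ADA concern is therefore confined to the main SAP's tables, and the listing gap for ADA may already be closed.

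**Conclusion.** The point holds in a limited form. The PDS wording removes early leavers with valid post-baseline samples from the PD, PK/PD, exploratory biomarker and main-SAP ADA summaries and from two listings, unless blind review decides otherwise. This is hard to square with Protocol 5.2.

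Each unreplaced active leaver would cost 16.7% of a dose group and widen the SEM by about 10%, assuming the SD is unchanged. The 71 to 89 day gap assumes that completion means the D90 visit, which Protocol 5.4 favours but does not tie to the PDS. How many participants, if any, would be lost cannot be told from the documents.

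A reader might infer that the trial's safety conclusion is at risk. It is not: adverse events, safety aPTT, creatinine and urea are analysed on the Safety set. What can be affected are descriptive secondary PD results and exploratory results. The change is still worth making, because it removes a possibly informative post-dose exclusion at little cost.

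**What to change.** - In SAP 7.1, delete the completion condition from the PDS. Membership then rests on being dosed, having at least one available post-baseline PD value, and having no protocol deviation affecting PD evaluation. Add no baseline requirement, which could newly exclude participants; compute changes from baseline wherever a baseline exists.
- Align section 3.2 of the August 2020 SAP appendix.
- Produce listings 16.2.6.1 and 16.2.6.2 on the Randomised set, as is done for plasma concentrations, so that the values of anyone still excluded can be seen.
- Record the departure from Protocol 10.2.3.1 in SAP section 5.

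Moving ADA and the biomarkers to the Safety set is not needed. Once the condition is gone, leavers with a post-baseline PD value and no PD-relevant deviation are in the PDS. The move would also switch these outputs from as-randomised to as-treated and depart from Protocol 10.2.9.2.

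The cost is SAP wording, a population flag and output titles, with no new data. The downside is that some incomplete profiles enter the summaries, so the number contributing may vary by time point.
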